10 ADDITIONAL INFORMATION

10.1 Ethical Conduct of the Study

The study will be performed in accordance with the protocol and consistent with ICH Good Clinical Practice (GCP) Guidelines and applicable DoD and local regulatory requirements and laws.

10.2 IRB Oversight

The study (protocol, informed consent form, recruiting materials, and any documents seen by the subject) will be reviewed and approved by the WRAIR IRB. Subjects will not be recruited, consented, screened, or enrolled until the IRB has approved the required documentation. In addition, the IRB will review amendments to the protocol before their implementation.

The Investigator will retain all correspondence with the IRB in the trial master file (TMF) and forward copies of all IRB approvals to the Sponsor.

10.3 Informed Consent

The Sponsor or designee will provide a master informed consent form (ICF) template to each site for development of a site-specific ICF.

All site-specific ICFs must be approved by the Sponsor or designee and the IRB and must be in compliance with ICH GCP, DoD and local regulatory and legal requirements. The Sponsor or designee will advise the Site of required changes to the master ICF template during the course of the study.

The Investigator will ensure that each potential study participant is fully informed about the nature and objectives of the study and possible risks associated with participation. Before informed consent is obtained, the Investigator, or a qualified person designated by the Investigator, will provide the potential study participant with ample time and opportunity to inquire about the details of the trial, and will answer all relevant questions to the potential study participant's satisfaction. The potential study participant will then decide whether or not to participate in the trial. The Investigator, or a qualified person designated by the Investigator, will obtain written informed consent from each study participant before any study-specific activity is performed.

The Investigator will retain the original and any amended signed and dated Informed Consent Form(s) at the study site and provide a copy to each study participant.

All informed consent forms also address the subject of the Genetic Information Nondiscrimination Act of 2008 (Pub. L. 110-233), also known as GINA. Participants will be advised that GINA is a federal law that prohibits discrimination in health insurance coverage and employment based on genetic information. However, GINA does not apply to employers with fewer than 15 employees.

GINA's protections in employment do not extend to the US military. Nor does it apply to health insurance through the TRICARE military health system, the Indian Health Service, the Veterans Health Administration, or the Federal Employees Health Benefits Program. Lastly, the law does not cover long term care insurance, life insurance or disability insurance.

The language in the study ICFs state as follows: "Though not currently planned, some future research studies may include genetic testing of research samples. This means that some of your DNA may be sequenced in order to, for example, learn how our DNA influences how we respond to vaccines. Using new technology, information about your DNA structure (genetic information) gained from your samples could be used to indicate your risk for developing certain diseases. This genetic information is unique to you and may indicate changes in your future health status or life expectancy, or that of your children and other relatives. There is growing concern that such information could be used by employers or insurance companies to discriminate against you. However, if we do this sort of testing, we will not share the results with you or knowingly make your samples available to your future employers or insurance companies."

10.4 Subject Confidentiality

The Investigator will ensure that each subject's anonymity is maintained. On eCRFs and other documents submitted to the Sponsor and/or its designee, subjects must be identified by subject number only. For documents that are not for submission to the Sponsor and/or its designee (e.g., signed ICFs), the Investigator must maintain these documents securely and in compliance with all federal laws and regulations, and ICH GCP Guidelines.

The Investigator will be responsible for retaining sufficient information about each subject, i.e., name, address, telephone number, Social Security number, and subject identifier in the study, so that the Sponsor's representative, the WRAIR IRB, the FDA, employees of USAMRDC, or other regulatory authorities may have access to this information should the need arise.

It is the policy of the USAMRDC that data sheets are to be completed for all subjects participating in research (Form 60-R, Volunteer Registry Data Sheet). The data sheets will be entered into this Command's Volunteer Registry Database. The information to be entered into this confidential data base includes the subject's name, address, and Social Security Number; study title; and dates of participation. The intent of this data base is twofold: first, to readily answer questions concerning an individual's participation in research sponsored by USAMRDC; and second, to ensure that USAMRDC can exercise its obligation to ensure research subjects are adequately warned (duty to warn) of risks and to provide new information as it becomes available. The information will be stored at USAMRDC for a minimum of 75 years. The Volunteer Registry Database is a separate entity and is not linked to the study database.

10.5 Compensation for Injury

All nonexempt research involving human subjects shall, at a minimum, meet the requirement of 32 CFR 219.116(a)(6). Namely, the Informed Consent document will not “include any exculpatory language through which the subject or the legally authorized representative is made to waive or appear to waive any of the subject’s legal rights, or releases or appears to release the investigator, the sponsor, the institution, or its agents from liability for negligence.”

If a subject is injured because of participation in this research, whether or not they are a DoD healthcare beneficiary, the subject is entitled to medical care for that injury at a military hospital or clinic; medical care charges for care at a military hospital or clinic will be waived. It cannot be determined in advance which military hospital or clinic will provide care. If the subject obtains care for research-related injuries outside of a military hospital or clinic, the subject or the subject’s insurance will be responsible for medical expenses. Transportation to and from DoD hospitals or clinics will not be provided, except in emergencies or situations where a non-DoD healthcare beneficiary requires a military escort for access to said hospitals or clinics. No reimbursement is available if the subject incurs medical expenses to treat research-related injuries. No compensation is available for research-related injuries. The subject is not waiving any legal rights. The subject should contact the PI if the subject believes he or she has sustained a research-related injury. The subject should contact the PI for any questions.

10.6 Clinicaltrials.gov

For purposes of reporting to clinicaltrials.gov, the Sponsor is the responsible party and will provide information regarding this study in accordance with applicable regulations.

10.7 Public Disclosure and Publication Policy

All publication rights are delineated in the Clinical Study Agreement.

10.8 Amendments

The protocol may be amended only by the Sponsor (Emergent Travel Health Inc.). All amendments and modifications will be reviewed and approved by the principal investigator, the sponsor’s representative. Amendments and modifications will then be submitted through the WRAIR HSPB for review by the WRAIR IRB and, if necessary, by the WRAIR Scientific Review Committee (SRC). WRAIR IRB approval of protocol amendments is required prior to implementation. A copy of all approval memos and approved protocol documents, including those associated with future protocol amendments, will also be submitted to USAMRIID for review and filing by the local Office of Human Research Oversight (OHRO) as well as review by and filing in the SIP Clinic on site regulatory files.

The informed consent must be revised to ensure alignment with any amendment as appropriate and must also be reviewed and approved by WRAIR IRB. If a significant change is made to the

protocol and informed consent, any subject already enrolled in the study will be informed about the revision and asked to sign the revised informed consent. A copy of the revised, signed, and dated informed consent will be given to the subject. All original versions of the informed consent will be retained in the protocol regulatory file and a copy will be retained in the clinic medical record.

APPENDIX A: SCHEDULE OF EVENTS

Study Event ¹	Screen	Day 1	Day 8	Day 22	Day 29	Day 57	Day 113	Day 182	Early DC
Compliance Ranges	-60 to -1	NA	+3 days	±3 days	±3 days	±7 days	±10 days	±14 days	
Informed Consent	X								
Vital signs	X	XX ⁸	X	X	X	X ⁹	X ⁹	X ⁹	X ⁹
Review Inclusion/Exclusion Criteria	X	X							
Screening Medical History to include prior/concomitant medications	X								
Physical Examination	X								
Interim medical history, solicited ² and unsolicited ³ AEs, and concomitant medications		X	X	X	X				X
Memory aid distribution		X							
Memory aid collection and review			X						If < D8
Clinical check ⁴		XX ⁸	X	X	X	X	X	X	X
CBC ⁵	X	X	X						If < D8
Creatinine, AST, ALT ⁵	X	X	X						If < D8
Anti-HIV-1/2, Anti-HCV, HBsAg, HBcAb, HBsAb	X								
Urine pregnancy test ⁶	X	X			X				If < D29
Sera for antibody assays/future use ⁷		X	X	X	X	X		X	X
Collection of blood for Peripheral Blood Mononuclear Cells (PBMCs)		X	X		X	X		X	
Minimum volume of blood required	24.5 mL	84.5 mL	84.5 mL	17 mL	57 mL	77 mL	0 mL	77 mL	0 to 20 mL
Cumulative volume of blood required (approximate mL)	30	120	210	230	290	370	370	450	n/a
Vaccination		X							

¹ SAE's will be collected throughout the study

² Solicited AEs collected through Day 8 only.

³ Unsolicited AEs collected through Day 29 only.

⁴ Clinical checks: targeted physical exams based on AEs/SAEs identified

⁵ CBC, Creatinine, AST, ALT will be collected but the results will not be included in the database.

⁶ Urine pregnancy tests only for women of child-bearing potential.

⁷ Antibody assays vary with time point but include NT₈₀ to CHIKV, PRNT₈₀ to VEEV, total antibodies to CHIKV and VEEV, and exploratory assays of humoral immunity.

⁸ On vaccination day, vital signs and clinical checks will occur twice: before and 30 to 60 minutes after vaccination.

⁹ Vital signs may be collected at the discretion of the investigator past Day 29 but will not be included in the database.

APPENDIX B: TOXICITY GRADING SCALE

EVENT	MILD (Grade 1)	MODERATE (Grade 2)	SEVERE (Grade 3)	POTENTIALLY LIFE THREATENING (Grade 4)
Fever	> 100.4 – 101.1°F (≥ 38.0 – 38.4°C)	≥ 101.2 – 102°F (≥ 38.5 – < 39°C)	≥ 102.1°F – 104°F (≥ 39°C – 40°C)	> 104°F (> 40°C)
Headache	No interference with activity	Some interference with activity, may require repeated use of non-narcotic pain reliever for more than 24 hours	Significant, prevents daily activity, any use of narcotic pain reliever	ER visit or hospitalization
Fatigue	No interference with activity	Some interference with activity	Significant, prevents daily activity	ER visit or hospitalization
Myalgia	No interference with activity	Some interference with activity	Significant, prevents daily activity	ER visit or hospitalization
Nausea	No interference with activity	Some interference with activity	Significant, prevents daily activity	ER visit or hospitalization for hypotensive shock
Vomiting	1–2 episodes/24 hours	> 2 episodes/24 hours	Requires IV hydration	ER visit or hospitalization for hypotensive shock
Diarrhea	2 – 3 loose stools or < 400 gms / 24 hours	4 – 5 stools or 400-800 gms/24 hours	6 or more watery stools or > 800 gms/24 hours or requires outpatient IV hydration	ER visit or hospitalization
Injection site pain	Does not interfere with activity	Repeated use of non-narcotic pain reliever > 24 hours or interferes with activity	Use of any narcotic pain reliever or prevents daily activity	ER visit or hospitalization
Injection site erythema/redness	25-50 mm	>50 mm – 100 mm	> 100 mm	Necrosis or exfoliative dermatitis
Injection site induration/swelling	25-50 mm and does not interfere with activity	>50 mm – 100 mm or interferes with activity	> 100 mm or prevents daily activity	Necrosis
Hgb (decrease from baseline value in gm/dL)	FEMALE: Any decrease – 1.5 MALE: Any decrease – 1.5	FEMALE: >1.5 – 2.0 MALE: >1.5 – 2.0	FEMALE: >2.0 – 5.0 MALE: >2.0 – 5.0	FEMALE: > 5.0 MALE: > 5.0
WBC increased	10,800 – 15,000 cells/mm ³	> 15,000 – 20,000 cells/mm ³	> 20,000 – 25,000 cells/mm ³	> 25,000 cells/mm ³
WBC decreased	2500 – 3500 cells/mm ³	1500 – < 2500 cells/mm ³	1000 – < 1500 cells/mm ³	< 1000 cells/mm ³
Lymphocytes decreased	750 – 1000 cells/mm ³	500 – < 750 cells/mm ³	250 – < 500 cells/mm ³	< 250 cells/mm ³

(cont'd)

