4.11 Solicited Adverse Events

Solicited AEs will be collected for 7 days after the injection. AEs that correspond to solicited AE terms but occur outside of (or continue past) the solicited AE collection period are also collected through the unsolicited AE reporting period. Solicited adverse events for this study are local events of pain, redness, and swelling at the injection site and systemic events of fever with oral temperature ≥ 100.4 F, chills, malaise, fatigue, headache, myalgia, arthralgia, and nausea.

Subjects will be trained to complete a memory aid to observe, measure, and record these solicited AEs. To measure oral temperature, a digital thermometer will be provided to the subject to measure their temperature each day and record them in their memory aid. To record injection site local reactions, a ruler will be provided to the subject to measure the diameter of redness or swelling at the largest point of the reaction each day and record them in their memory aid.

Study staff will review the signs and symptoms recorded on the memory aid and the action taken for the event at subsequent visits. The memory aid will be collected and maintained in the subject file but the final determination of each adverse event name, onset and resolution dates, severity and causality will be made by the Investigator. Severity will be graded according to the Toxicity Grading Scale (Appendix B). The results of the Investigator's assessment will be recorded as a separate source document from the memory aid and will be entered on the corresponding (solicited) adverse event eCRF.

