7.2. Adverse Events

An AE is any untoward medical occurrence in a study participant, regardless of the suspected causal relationship with study vaccine. An AE can therefore be a new-onset symptom or disease, an exacerbation of a pre-existing symptom or disease, a new-onset laboratory abnormality considered by the Investigator to be clinically significant, a new-onset symptom or disease that occurs as a result of a protocol-specified procedure.

The reporting period for SAEs begins at the time of informed consent and continues for the duration of study participation. The reporting period for solicited AEs begins after study vaccine administration on Day 1 and continues through Day 8. The reporting period for unsolicited AEs begins after study vaccine administration on Day 1 and continues through Day 29.

Solicited AEs are assigned to two different categories of events, systemic and local, with the following pre-specified signs and symptoms:

1. Systemic events: fever with oral temperature ≥ 100.4 °F, chills, malaise, fatigue, headache, myalgia, arthralgia, and nausea
2. Local events: pain, redness, and swelling at the injection site

Solicited AEs from Day 1 through Day 8 will be recorded on the solicited AE electronic case report form (eCRF). Symptoms experienced on Day 8 and continuing beyond Day 8 will be recorded on the AE eCRF with a start date corresponding to the first date the symptom was continuously experienced through Day 8.

An unsolicited AE is defined as an AE that is spontaneously reported by the subject or discovered by the Investigator.

Adverse Event Dictionary

AEs will be coded using the MedDRA version 20.1. SOC, High Level Group Term (HLGT), High Level Term (HLT), PT, and Lowest Level Term (LLT) will be attached to the clinical database.

All solicited AEs will be summarized according to severity grading scales defined in Sections 6.2 and 9.5.1 of the protocol; these range from “mild” to “potentially life-threatening.”

The analyses of solicited AEs (categorized as systemic or local) will be tabulated by maximum severity and study arm. In addition, solicited AEs ongoing after 7 days post-injection will be also recorded as unsolicited AEs. Frequencies and percentages of subjects experiencing each solicited AE will be presented by maximum severity.

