7.2.1. Adverse Event Severity

AEs (inclusive of all solicited and unsolicited AEs) are graded by the Investigator or designee as Grade 1 (mild), Grade 2 (moderate), Grade 3 (severe) or Grade 4 (potentially life-threatening) according to toxicity criteria specified in the study protocol (see Appendix B of study protocol). The severity grade of events for which the Investigator did not record severity will be categorized as “missing” for tabular summaries and data listings, and will be considered the least severe for the purposes of sorting for data presentation (will sort to the top).

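### The Fahrenheit and Celsius limits in the fever row of Appendix B are not equivalent, and the Fahrenheit start of Grade 1 misses the lowest temperature that counts as solicited fever

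*Protocol*

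**What the plan says.** Protocol section 4.11 lists, among the solicited systemic events, "fever with oral temperature ≥ 100.4 F". SAP section 7.2 uses the same inclusive threshold: "Systemic events: fever with oral temperature ≥ 100.4 °F, chills, malaise, fatigue, headache, myalgia, arthralgia, and nausea". Both definitions are in Fahrenheit only.

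On severity, protocol section 4.11 states: "Severity will be graded according to the Toxicity Grading Scale (Appendix B". SAP section 7.2.1 likewise has events graded "according to toxicity criteria specified in the study protocol (see Appendix B of study protocol".

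The fever row of Appendix B gives each grade in Fahrenheit with Celsius in parentheses:

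- Grade 1: "> 100.4 – 101.1°F (≥ 38.0 – 38.4°C"
- Grade 2: "≥ 101.2 – 102°F (≥ 38.5 – < 39°C"
- Grade 3: "≥ 102.1°F – 104°F (≥ 39°C – 40°C"
- Grade 4: above 104°F (above 40°C)

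Neither document says which unit governs. The note under Appendix B says that the sponsor adjusted some published limits so that no gaps remain between grades. Section 4.11 gives each subject a digital thermometer and does not state its unit.

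**The concern.** An event definition and the scale that grades it should start at the same value, and limits printed in two units in one cell should describe the same temperatures. Neither holds here. The definition includes 100.4°F, while the Fahrenheit side of Grade 1 begins strictly above it. The Grade 2 and Grade 3 lower limits also differ slightly between the units.

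What could change is the classification of fever by severity. SAP section 7.3.1 tabulates solicited events by maximum grade and repeats the summary for Grade 3 or higher, with a Fisher's exact test between arms (Tables 14.3.1.1 and 14.3.1.2, both listed for revision in SAP Addendum 2). A reading of 102.1°F belongs in the Grade 3-or-higher table by one unit and not by the other.

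**Working it through.** **Inputs.** The fever definition comes from protocol section 4.11 and SAP section 7.2, and the grade limits from the fever row of Appendix B. The conversion is °C = (°F − 32) × 5/9.

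**Celsius limits converted to Fahrenheit** (°F = °C × 9/5 + 32):

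- 38.0°C = 100.4°F
- 38.4°C = 101.12°F
- 38.5°C = 101.3°F (the printed Fahrenheit limit is 101.2)
- 39°C = 102.2°F (the printed Fahrenheit limit is 102.1)
- 40°C = 104.0°F

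The temperatures at 38.0°C and 40°C pair exactly. At 38.0°C the mismatch is only in the inequality sign. The lower limits of Grades 2 and 3 are each 0.1°F apart between units.

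**Grading every 0.1°F reading from 100.2 to 104.2 both ways.** That is 41 readings. The Celsius grade was taken once from the exact conversion and once after rounding to 0.1°C. Three readings disagree:

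| Reading | Exact °C | °C to 0.1 | Grade by °F limits | Grade by °C, exact | Grade by °C, rounded |
|---|---|---|---|---|---|
| 100.4°F | (100.4 − 32) × 5/9 = 38.00 | 38.0 | none | 1 | 1 |
| 101.2°F | (101.2 − 32) × 5/9 = 38.44 | 38.4 | 2 | none (between 38.4 and 38.5) | 1 |
| 102.1°F | (102.1 − 32) × 5/9 = 38.94 | 38.9 | 3 | 2 | 2 |

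The other 38 readings receive the same result in all three columns, including 104.0°F (40.0°C), which is Grade 3 in both units.

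**How often this could matter.** Protocol section 1.2.2.3 reports fever in 1.7% of subjects after any injection in the earlier phase 2 study. Applied to 60 subjects, 60 × 0.017 = 1.02, or about one subject with any fever. This is an extrapolation, because that figure covers several regimens and any injection, while this study gives one injection. That subject's maximum temperature would also have to fall on one of the three readings.

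**Effect on the comparison between arms.** Suppose one subject in all were classed as Grade 3 fever, with 30 per arm. Given a single event, it falls in either arm with probability 30/60 = 0.5. The two possible tables are equally likely, so the two-sided Fisher p-value is 0.5 + 0.5 = 1. Moving that subject in or out of the row changes a printed count, not an inference.

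**The case against.** The strongest reply is that the scale works in practice. Both sites are in the United States, the fever definition is in Fahrenheit, and Appendix B prints Fahrenheit first. Read in Fahrenheit alone to 0.1°, the grades are contiguous above 100.4. Read in Celsius alone to 0.1°, they are contiguous throughout. A conflict at 101.2 or 102.1 needs someone to convert a reading and grade it by the parenthesis, or to use a Celsius thermometer, and neither document plans either. This stands as a limit on the size of the problem. It does not make the paired limits equivalent, and it leaves the mismatch at 100.4°F, which lies within Fahrenheit itself.

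The sign before 100.4 might also be a fault of text extraction. That cannot be excluded, but the same row prints the inclusive sign elsewhere, and the 101.2°F and 102.1°F mismatches do not depend on it.

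Three stronger readings are tempting, and the documents do not support them:

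- **That 100.4°F has no grade at all.** It has none by the Fahrenheit limits only. The Celsius limit in the same cell makes it Grade 1.
- **That such a reading becomes a missing severity in the tables.** SAP section 7.2.1 assigns that category only when the Investigator recorded no severity. Protocol sections 4.11 and 6.2 require the Investigator to grade every event, so a grade would be expected.
- **That the arms could be graded differently because each is seen at its own site.** Nothing shows that either site used Celsius or that the two sites used different units. The unstated thermometer unit is a small gap, not evidence of differential grading.

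**Conclusion.** The point holds as an inconsistency in an operative grading rule. By the printed limits, three 0.1°F readings (100.4, 101.2 and 102.1) are classified differently according to unit, and the lowest solicited fever has no Fahrenheit grade. This rests on the limits as printed and on temperatures read to 0.1°.

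The consequence is minor. Only the split of fever by severity and the table of solicited events of Grade 3 or higher could move, probably by no more than one subject. Fever incidence and its comparison between arms use the 100.4°F definition, which is the same in both documents. The stopping rule in protocol section 6.8 depends on related serious adverse events, not on fever grade. The primary immunogenicity endpoint is not involved. The documents do not show that any subject was misgraded.

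**What to change.** Reconcile the fever row of Appendix B with the solicited-fever definition so that every solicited fever has a grade. State which unit governs grading, and either convert the other unit exactly, leaving no gap between grades, or delete it. Which limits to keep is for the sponsor to decide.

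The Investigator's grading in protocol sections 4.11 and 6.2 should stay. Deriving the grade by program is not needed: it would displace that assessment and would require daily temperatures in the database, which section 4.11 does not describe.

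The cost is one table row and one sentence naming the unit. SAP Addendum 1 shows that the database has already been locked, so for this trial a footnote to Tables 14.3.1.1 and 14.3.1.2 naming the unit used for grading would serve, with the corrected row carried into any later protocol that reuses the scale.
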